7.4 Measures to Minimize Bias

7.4.1 Enrollment/Randomization/Masking Procedures

Blocked stratification will be used to randomize the participants to their respective study conditions. Block sizes of 4 and 6 will be used and the stratifying factor will be EDSS score (0-3.5 and 4.0-6.5).

For the purposes of masking, the two conditions will be indistinguishable by the participant and administering study technician as all that separates the two conditions will be the sham tDCS. Sham tDCS is very effective in making participants believe they are receiving true treatment. A separate study technician or study PI will prepare the participant's condition so as to ensure the double blind.

CONFIDENTIAL

This material is the property of the NYU School of Medicine and Langone Medical Center. Do not disclose or use except as authorized in writing by the study sponsor

Interventional Template Version: 28 APR 2017

7.4.2 Evaluation of Success of Blinding

Participants will be asked at the end of the study what condition they believed they were assigned to: Active, sham, or that they cannot determine which.

7.4.3 Breaking the Study Blind

Study blind will be broken at the participation end visit.

8 Source Documents and Access to Source Data/Documents

The study case report form (CRF) is the primary data collection instrument for the study. All data requested on the CRF must be recorded. All missing data must be explained. If a space on the CRF is left blank because the procedure was not done or the question was not asked, write "N/D". If the item is not applicable to the individual case, write "N/A". All entries should be printed legibly in black ink. If any entry error has been made, to correct such an error, draw a single straight line through the incorrect entry and enter the correct data above it. All such changes must be initialled and dated. DO NOT ERASE OR WHITE OUT ERRORS. For clarification of illegible or uncertain entries, print the clarification above the item, then initial and date it.

Access to study records will be limited to IRB-approved members of the study team. The investigator will permit study-related monitoring, audits, and inspections by the IRB/EC, the sponsor, government regulatory bodies, and University compliance and quality assurance groups of all study related documents (e.g. source documents, regulatory documents, data collection instruments, study data etc.). The investigator will ensure the capability for inspections of applicable study-related facilities (e.g. pharmacy, diagnostic laboratory, etc.).

Participation as an investigator in this study implies acceptance of potential inspection by government regulatory authorities and applicable University compliance and quality assurance offices.

9 Quality Assurance and Quality Control

Quality control procedures will be implemented beginning with data entry on NYULH's REDcap system. Any missing data or data anomalies will be communicated to the site(s) for clarification/ resolution to ensure quality of data.

10 Ethics/Protection of Human Subjects

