3.4 Study Endpoints

3.4.1 Primary Study Endpoints

To determine the efficacy of the combination of tDCS and physical training, the following primary outcome measures have been chosen:

- Efficacy measured by comparison between the active and sham conditions by comparing the changes in gait velocity and stride length at baseline and participation end
- Compliance measured by 80% of participants having completed the study sessions

CONFIDENTIAL

This material is the property of the NYU School of Medicine and Langone Medical Center. Do not disclose or use except as authorized in writing by the study sponsor

Interventional Template Version: 28 APR 2017

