4.4 Duration of Study Participation

Participants will complete study activities for approximately 5 to 7 hours total over the course of 10 sessions.

> The baseline visit will last approximately 1.5-2 hours (30 minutes to consent, 60 minutes for baseline measures and 20 minutes for tDCS session 1) minutes where initial study measures are administered.

At the baseline visit, participants may be provided with a wristwatch accelerometer ActiGraph. They will be asked to wear the ActiGraph wristwatch for the entire study duration until the follow-up visit, except for during water-related events such as bathing, showering and swimming. The first tDCS and PA session will be scheduled from 4 to 7 days after the baseline visit. During this window of time (baseline to first study session), participants daily activity will be recorded through the ActiGraph wristwatch. Due to the limited availability of study actigraph devices, use of the ActiGraph will be optional and at the discretion of study staff. If the Actigraph is not being used then the first session will occur same day as baseline.

> Remote study sessions 2 through 10 will be approximately 20 minutes in duration, as follows: 20 min: tDCS (active or sham) session while performing PA program lasts 20 min (cycling paired with simultaneous tDCS)

*** Please note that while 10 sessions will be scheduled consecutively across a two-week period, the participant will be able to complete any missed sessions during the 3rd week.**

> Follow-up (Visit 11) will take approximately 1 hour to repeat baseline measures.

> A final follow-up visit will be approximately 1 hour after around four weeks from the end of the treatment. Participants will return the wristwatch accelerometer (ActiGraph) at the follow-up visit and complete gait assessment and self-reported questionnaires.

	Gait and Balance assessment and self-report questionnaires	Gait, Balance, and Functional mobility Measures	EEG with Cognitive Testing*	tDCS (active or sham) + PA	Actigraph Wristwatch Assigned*	Actigraph Baseline*	Actigraph Wristwatch Returned*
Baseline	x				x*	x*	
Session 1		x	x*	x			
Session 2		x		x			
Session 3	x			x			
Session 4	x			x			
Session 5	x			x			
Session 6	x			x			
Session 7	x			x			
Session 8	x			x			
Session 9		x	x*	x			
Session 10	x			x			
Treatment-End Visit	x		x*				x*
Follow-up (4 weeks ± 1 week post-	x*						

CONFIDENTIAL

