5.3.3 Intermediate Remote Visits (Day 2 to Day 10)

- Administer the study treatment for 9 visits
(Active stimulation: 20 mins of tDCS (2.5mA) while participants will complete physical training; Sham stimulation: 20 mins of tDCS sham stimulation, no current delivery during the session, while participants will complete physical training)
- Record adverse events as reported by participant with pain ratings (VAS- P₁₋₁₀) and self-reporting and rating possible adverse events during each stimulation session
- Monitoring of perceived exertion using Borg scale. Borg scale will be administered by study technician every 5 minutes during the 20 minutes PA training
- Instructions provided to participants after the session: no concurrent physical therapy for the entire duration of the study
- Optional: Only for the first (day 1) and follow-up (day 11) may participants' be asked to wear EEG electrodes. While performing cognitive tests (CogState and the SDMT) before and after the stimulation period, participant's EEG signals will be simultaneously recorded for ten minutes.

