5.3.4 Treatment End visit (within 3 days after session 10)

- Gait assessment with instrumented 10-meter walk (i-10MW), functional mobility assessment with instrumented Time Up and GO (i-TUG), Timed 25-Foot Walk (T25-FW), instrumented 2 minute walk (i-2MW) test, balance assessment with static posturography test, administration of Berg Balance Scale, and administration of questionnaires (9-item FSS, 21-item MFIS, MSWS-12, 54-MSQOL, and VAS- F 0-10)
- Cognitive assessment using BICAMS and CogState brief battery

5.3.5 Final Study Visit (within 4 ± 1 weeks from the end of treatment i.e. Session 10)

- Gait assessment with instrumented 10-meter walk (i-10MW), functional mobility with instrumented Time Up and GO (i-TUG), and balance assessment with static posturography test, administration of Berg Balance Scale, Timed 25-Foot Walk (T25-FW)
- Administration of questionnaires (9-item FSS, 21-item MFIS, MSWS-12, 54-MSQOL, and VAS- F 0-10)
- Record participant's adherence to treatment program
- Cognitive assessment using BICAMS and CogState brief battery
- Collect the ActiGraph device (Optional)

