6.4.4 Reporting of Pregnancy

Participants that become pregnant during the course of the study will be discontinued from treatment and will be asked to complete a concluding participation end visit that includes no risk or involvement of treatment. Only assessment will occur at the participation end visit.

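### Section 7.4.3 ties unblinding to a visit that no supplied schedule names and sets no last-participant or database-lock condition; separately, section 7.4.1 lets the PI prepare the allocated condition although the investigator is to be masked

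*Combined protocol and SAP*

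**What the plan says.** **Unblinding.** Section 7.4.3 consists of one sentence: "Study blind will be broken at the participation end visit". It gives no other condition and does not say who learns the assignment.

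**The term.** The same visit name appears in section 6.4.4, where a participant who becomes pregnant is "asked to complete a concluding participation end visit that includes no risk or involvement of treatment". There it means that person's own last assessment, at whatever point it falls. Section 3.4.1 uses a related phrase for the primary efficacy endpoint: "comparing the changes in gait velocity and stride length at baseline and participation end". Section 7.1 places the active-sham comparison at baseline and the end of treatment.

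**Visits after treatment.** Section 5.3.4 has a treatment-end visit within 3 days of session 10. Section 5.3.5 has a final visit 4 ± 1 weeks after session 10. Section 4.4 calls the first of these Visit 11 and describes the second thus: "A final follow-up visit will be approximately 1 hour after around four weeks from the end of the treatment". The tables in sections 4.4 and 16 mark the 4-week visit as optional.

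**Analysis.** Section 7.2.2 analyses gait speed and stride length by repeated-measures ANOVA with three Time levels: day 1, day 10 and four weeks.

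**Masking.** The Protocol Summary masks participant and investigator. Section 3.3 masks participant and study staff, and gives randomization to an independent person with no part in baseline, follow-up or sessions. Section 7.4.1 has the condition prepared by either a separate technician or the PI.

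**The concern.** An unblinding rule should fix one moment and say who is told. This one attaches the break to an individual's visit, under a name that the supplied schedules do not contain. Two things are at stake.

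First, opening codes participant by participant in a single-site trial with small stratified blocks gives anyone who both recruits and sees opened codes some information about allocations still to come.

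Second, if the break falls at treatment end, the 4-week self-reports, self-selected walking speed and the assessor-scored Berg scale would be collected from people who know their arm. Attendance at that optional visit could then depend on the arm as well.

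The preparer clause is a separate matter. A PI who sets up a participant's condition knows that allocation from the start. The PI also joins weekly reviews of each subject's clinical course and assessments (section 6) and may remove participants (section 6.5).

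**Working it through.** **1. Which visit is meant?** The plan states no figure here, so the check is a comparison of passages.

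| Source | First visit after treatment | Second visit after treatment |
|---|---|---|
| 4.4 text | Follow-up (Visit 11) | final follow-up visit, about four weeks later |
| 4.4 table | Treatment-End Visit | Follow-up, optional |
| 5.3.4 and 5.3.5 | Treatment End visit | Final Study Visit |
| 16 | Study visit 11 / Treatment End Visit | Follow-up visit, optional |

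None is called a participation end visit. Part of section 5 is absent from the supplied text, so this holds for the supplied schedules only.

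**2. Two readings.**

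- *Treatment end.* Sections 3.4.1 and 7.1, read together, equate the end of participation with the end of treatment. The 4-week measurements then follow the break: 1 of the 3 Time levels in section 7.2.2.
- *The participant's last visit.* Section 6.4.4 favours this. No Time level of that participant is then shown to be unblinded. Because the 4-week visit is optional, someone who skips it has no clear unblinding time.

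Under both readings the trigger is an individual's visit, so codes may open while others are still in the trial.

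**3. Who prepares the condition?** Section 7.4.1 calls the conditions indistinguishable to the participant and the administering technician only. Nothing keeps a PI who prepares the condition masked. That conflicts with investigator masking in the Protocol Summary.

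**4. Illustration of participant-by-participant opening.**

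*From the protocol:* 80 participants, two EDSS strata, blocks of 4 and 6.

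*Assumed:* even accrual over 12, 24 or 48 months; equal strata; both block sizes equally likely; one person who recruits and sees every code as it opens. That person knows the blocks are 4 or 6, but not which size applies or where a block begins.

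Lag from baseline to break, from the visit windows in sections 4.4, 4.9.1, 5.3.4 and 5.3.5:

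- treatment end, shortest: session 1 on the baseline day, 10 business days from a Monday, visit on the last day = 11 days
- treatment end, longest: 7 + 21 + 3 = 31 days
- 4-week visit, shortest: 11 + 21 = 32 days
- 4-week visit, longest: 7 + 21 + 35 = 63 days

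Let *a* and *b* be the active and sham places left in the current block, and *w(a,b)* the probability of that state given the opened codes, averaged over codes not yet opened. Then P(next is active) = Σ *w(a,b)* · *a*/(*a*+*b*). An allocation is fully determined when this is 0 or 1. Simulated share fully determined (4,000 replicates per cell):

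| Lag | 12 months | 24 months | 48 months |
|---|---|---|---|
| 11 days | 3.1% | 4.2% | 5.0% |
| 31 days | 0.7% | 2.2% | 3.7% |
| 32 days | 0.7% | 2.2% | 3.8% |
| 63 days | 0.03% | 0.7% | 2.2% |

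The range is about 0-5%. Section 16 places randomization at screening, so true lags are longer and these shares are somewhat high.

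**The case against.** The strongest reply is that this is loose wording and that no harm is shown. Much of that stands.

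- A reader might infer that the 4-week data will be collected unblinded. The documents do not establish it: section 6.4.4 points to the participant's last visit. Even under the treatment-end reading, the baseline to treatment-end contrast of sections 3.4.1 and 7.1 precedes the break, provided that visit's measurements come before disclosure.
- A reader might infer that recruiters could predict allocations. That needs a person who both recruits and sees every opened code. No passage describes one, and section 3.3 gives randomization to an independent person. Larger shares, up to 22%, arise only if block boundaries are known, and nothing says that staff hold them.
- A reader might infer that the PI will be unmasked. Section 7.4.1 names the separate technician first and only permits the PI. Staff masking in section 3.3 does not single out the PI either, since a technician is also staff. The conflict specific to the PI is with investigator masking in the Protocol Summary.

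What does not fall away is the rule itself. Section 7.4.3 states a trigger, and following it literally opens codes during the trial. The independent randomizer does not cure the preparer clause, because preparation is assigned separately.

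**Conclusion.** The point holds as a cheap improvement, with moderate confidence. It rests on the text: an undefined trigger, no last-participant or database-lock condition in the supplied passages, no statement of who is told, and a preparer clause at odds with investigator masking.

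Its size depends on the reading. At treatment end, one of three Time levels in the primary analysis follows the break; at the last visit, none of that participant's own data is shown to be exposed. Participant-by-participant opening is permitted either way. The 0-5% share is an illustration under assumed accrual and an assumed observer. It is not evidence of a leak, and no bias in gait velocity has been estimated.

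**What to change.** 1. Replace the sentence in section 7.4.3 with one trigger: the blind is kept for participants and for recruiting, treating and assessing staff until the last participant's last visit and database lock, except for medical need.
2. Remove the PI as an alternative preparer in section 7.4.1. Leave preparation to the separate technician, who takes no part in that participant's sessions or assessments and is named in section 3.3 as the exception to staff masking.
3. As clarifications only: state which scheduled visit the end of participation means in the endpoints (Protocol Summary, 3.4.1 and 3.4.2); keep the visit in section 6.4.4 as a separate early concluding visit that does not trigger unblinding; and ask the allocation guess of section 7.4.2 before any disclosure.

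The cost is wording. No visits are added, and the separate technician is already in the plan. Participants wait longer to learn their assignment, and the PI is no longer available as back-up preparer.

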10.1 Ethical Standard

The investigator will ensure that this study is conducted in full conformity with Regulations for the Protection of Human Subjects of Research codified in 45 CFR Part 46, 21 CFR Part 50, 21 CFR Part 56, and/or the ICH E6.

10.2 Institutional Review Board

The protocol, informed consent form, recruitment materials, and all participant materials will be submitted to the IRB for review and approval. Approval of both the protocol and the consent form must be obtained before any participant is enrolled. Any amendment to the protocol will require review and approval by the IRB before the changes are implemented to the study. All changes to the consent form will be IRB approved; a determination will be made regarding whether previously consented participants need to be re-consented.

10.3 Informed Consent Process

All potential participants will complete a telephone pre-screening interview to ensure general eligibility. The study staff member speaking to the subject will provide the subject with an overview of the study and verbally receive their consent, under a waiver of documentation of consent, to complete the general eligibility screening. This phone screen is minimal risk to the participant and collected information will be maintained in secured,

CONFIDENTIAL

This material is the property of the NYU School of Medicine and Langone Medical Center. Do not disclose or use except as authorized in writing by the study sponsor

locked files. A study referral log created in Microsoft Excel, in compliance with institutional policy, will be used to track participant eligibility prior to the process of informed consent and formal entry into the CRMS system. If a participant is not eligible, they will be considered a screen fail. No additional information will be collected. PHI will be destroyed immediately if a participant is not eligible or does not return to sign written consent/authorization to participate. Only study staff will have access to these records. Once the participant is generally eligible, the PI, or one of the trained study team members will review the consent form with the subject and explain the purpose of the study, the procedures, as well as risks and benefits. All questions will be addressed before acquiring the participant's signed consent. [name] or one of the other IRB approved study physicians will be responsible for assessing the capacity to consent. We anticipate all eligible participants to have the capacity to consent and do not expect any participants to lose capacity to consent during the study. An independent assessor will not be utilized.

10.3.1 Consent/Accent and Other Informational Documents Provided to Participants

Informed consent is a process that is initiated prior to the individual's agreeing to participate in the study and continues throughout the individual's study participation. Extensive discussion of risks and possible benefits of participation will be provided to the participants and their families. Consent forms will be IRB-approved and the participant will be asked to read and review the document. The investigator will explain the research study to the participant and answer any questions that may arise. All participants will receive a verbal explanation in terms suited to their comprehension of the purposes, procedures, and potential risks of the study and of their rights as research participants. Participants will have the opportunity to carefully review the written consent form and ask questions prior to signing. The participants should have the opportunity to discuss the study with their surrogates or think about it prior to agreeing to participate. The participant will sign the informed consent document prior to any procedures being done specifically for the study. The participants may withdraw consent at any time throughout the course of the trial. A copy of the signed informed consent document will be given to the participants for their records. The rights and welfare of the participants will be protected by emphasizing to them that the quality of their medical care will not be adversely affected if they decline to participate in this study.

Consent forms describing in detail the study agent, study procedures, and risks are given to the participant and written documentation of informed consent is required prior to starting intervention/administering study product.

10.3.2 Consent Procedures and Documentation

A copy of the signed informed consent document will be stored in the subject's research record. The consent process, including the name of the individual obtaining consent, will be thoroughly documented in the subject's research record. Any alteration to the standard consent process (e.g. use of an interpreter, consent document presented orally, etc.) and the justification for such alteration will likewise be documented.

Process to Document Consent in Writing: After review of the consent form and prior to the start of the first session, the PI or one of the coinvestigators will obtain written consent with a signature of the patient on the consent form. All original signed consent forms will be maintained in the study file, separate from the participant data.

Subject Capacity: All participants will be confirmed to have the capacity to provide consent by [name] as described above. Further, those participants with estimated premorbid intellectual functioning and/or impaired reading ability (as determined by the WRAT-4 Reading Subtest) will be excluded.

Debriefing Procedures: No information will be purposely withheld from the subjects. A clinical neuropsychologist (PI) and the treatment team will be available to answer any questions concerning the tests and results, and provide initial feedback as warranted, including referral for clinical neuropsychological assessment.

Consent Forms: Participants will receive a NYU consent form to review and sign prior to participating in the study.

CONFIDENTIAL

This material is the property of the NYU School of Medicine and Langone Medical Center. Do not disclose or use except as authorized in writing by the study sponsor

Interventional Template Version: 28 APR 2017

Documentation of Consent: The PI is responsible for ensuring that valid consent is obtained and documented for all subjects. An enrollment log will be maintained and consent forms will be kept in secure location separate from the participant's data.

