3.3 Description of Study Design

This is an interventional, randomized, double-blind (participant and study staff), sham-controlled, parallel design, pilot study of N=80 RR-MS and SP-MS participants, characterized by mild to moderate gait dysfunctions. There will be a 1:1 random assignment of participants to receive either the active or the sham tDCS while performing the PA program. Blocked stratification will be used to randomize the participants to their respective study conditions. Block sizes of 4 and 6 will be used and the stratifying factor will be EDSS score (0-3.5 and 4.0-6.5). Randomization will be done by an independent randomizer who takes no part in baseline, follow-up, or sessions to maintain the double-blind nature of the study.

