4.3 Strategies for Recruitment and Retention

The MS Comprehensive Care Center of NYU Langone Medical Center has an extensive recruitment base. Patients will be recruited to participate in studies from all over New York and the other regions within the continental United States. Patients who are seen by medical staff at NYU Langone Medical Center, who fit the eligibility criteria, will be referred for the study by the study PI and sub-investigators. All physicians and medical staff at the MS Care Center will be presented with the study description.

A patient who is seeing one of these medical staff members as their treating physician will be introduced to the study by that medical staff member. If the patient is interested and agrees to be contacted by the study team, then a member of the study staff will contact them. Once a patient is identified, study staff will meet with the patient or call them to provide additional information regarding study participation. After the patient has reviewed

CONFIDENTIAL

This material is the property of the NYU School of Medicine and Langone Medical Center. Do not disclose or use except as authorized in writing by the study sponsor

Interventional Template Version: 28 APR 2017

the consent form and asked all questions, and provides consent to participate, the patient will be enrolled in the study.

Advertisements:

An IRB approved flyer will be posted in local physician offices and waiting rooms and throughout NYU, the surrounding community, and on Long Island. A description of the study will be posted on MS related websites

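### Section 7.4.1 lets the PI, who also refers and may consent participants, prepare their tDCS condition, so allocation concealment and investigator masking are not assured

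*Combined protocol and SAP*

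**What the plan says.** **Preparing the condition.** Section 7.4.1 states: "A separate study technician or study PI will prepare the participant's condition so as to ensure the double blind". Whoever does this knows the arm.

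**Enrolling.** Under 4.3, eligible patients seen at the center "will be referred for the study by the study PI and sub-investigators". Section 10.3 lets the PI or a trained team member go through the consent form with the candidate. Section 10.3.2 says "the PI or one of the coinvestigators will obtain written consent with a signature of the patient on the consent form".

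**Masking and randomization.** The Protocol Summary lists participant and investigator as masked, and 3.3 extends this to study staff. Section 3.3 gives randomization to an independent person who is kept out of the baseline visit, the treatment sessions and follow-up. It also gives the blocking: "Block sizes of 4 and 6 will be used", 1:1, within two EDSS strata.

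**Debriefing.** Section 10.3.2 says "No information will be purposely withheld from the subjects". It adds that the PI, a clinical neuropsychologist, and the treatment team "will be available to answer any questions concerning the tests and results, and provide initial feedback as warranted". It gives no time point and does not mention allocation.

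**The concern.** Read together, these sections allow one person to know which arm earlier participants received and to influence who enters next. That contradicts the masking stated in the Protocol Summary and 3.3. It also weakens concealment, because the block sizes and strata are printed in the protocol.

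Entry leaves room for judgment. Section 4.1 asks for clinical stability and clinically significant gait deviations, and 4.2 has an exclusion that depends on the opinion of the neurologist or staff. A recruiter who expects a given arm next could, without intending to, apply these differently. The resulting imbalance would sit in baseline prognosis, and masking the outcome assessors cannot remove it. It would reach the primary outcomes, gait velocity and stride length.

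The debriefing text raises a smaller matter. With no time set, a participant could be told at the treatment-end visit how gait, balance or cognition had changed, possibly by someone who knows the arm, and then complete the 4-week questionnaires. Those scores enter the three-time-point repeated-measures ANOVA in 7.2.3.

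**Working it through.** The plan gives no figure on this point, so there is none to reproduce. The check has three parts.

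**1. Roles side by side**

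| Task | Who may do it | Section |
|---|---|---|
| Generate allocation | Independent randomizer | 3.3 |
| Prepare condition (arm known) | Separate technician or PI | 7.4.1 |
| Refer | PI and sub-investigators | 4.3 |
| Review consent form | PI or trained team member | 10.3 |
| Take written consent | PI or co-investigator | 10.3.2 |
| Stated as masked | Participant, investigator, study staff | Protocol Summary, 3.3 |

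The PI is permitted in four of these tasks and masked by the last row. No section separates the tasks.

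**2. Predictability if the PI holds both roles throughout**

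Inputs from the documents: 1:1 allocation, blocks of 4 and 6, two strata, N = 80. Assumed: the two block sizes are equally likely, there are 40 participants per stratum, and every earlier assignment is known.

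The guessing rule is to name the arm that is behind and toss a coin when the arms are level. Balance returns to zero after each block, so the rule does not need block boundaries. For a block with m per arm, the expected number of correct guesses is

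m + 2^(2m−1) / C(2m, m) − 1/2.

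- Block of 4 (m = 2): 2 + 8/6 − 0.5 = 2.833, and 2.833/4 = 70.8%.
- Block of 6 (m = 3): 3 + 32/20 − 0.5 = 4.100, and 4.100/6 = 68.3%.
- Long-run equal mix: (2.833 + 4.100)/(4 + 6) = 69.3%.

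Simulation with each stratum cut off at 40, so that the last block may be incomplete, gives 68.9%. An optimal Bayesian guess gives the same result. Under concealment the figure is 50%.

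For certain assignments, suppose a stratum opens with three of the same arm. The block must be of size 6, so the next three are known. Counting every such case in the simulation gives 5.7%. If block boundaries were also known, the share would be 1/(m + 1): 33% in blocks of 4 and 25% in blocks of 6.

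Over 80 participants, this is about 0.689 × 80 = 55 correct guesses against 40 by chance, and about 0.057 × 80 = 4.6 certain assignments.

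**3. Timing of feedback**

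Baseline (5.3.2) is the first measurement, so feedback then cannot describe change. Gait, balance and cognition are next measured at treatment end (5.3.4), at the same visit as the questionnaires. The exposed data are therefore the questionnaires at 4 weeks (5.3.5).

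The longest wait from baseline to that visit is up to 1 week before session 1 when the ActiGraph is used (4.4), plus 3 weeks with make-up sessions (4.4), plus 4 + 1 weeks to follow-up (5.3.5). That is 1 + 3 + 5 = 9 weeks.

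**The case against.** **On roles.** The PI is only one permitted person in each role, and the independent randomizer produces the allocation. Preparing earlier conditions does not reveal the next one; it only improves the guess. Treating staff introduce patients and study staff pre-screen by telephone, so the PI does not control entry alone. All of this stands. A reader might infer that enrolment is not concealed, but the documents do not show that. An independent allocation list does not, however, protect concealment if past assignments reach the person who enrols, and no text prevents this.

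**On the 69%.** It requires the PI to prepare every condition and influence enrolment throughout. That is correct. It measures what the wording permits and does not forecast what will happen.

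**On debriefing.** A reader might take the debriefing sentence to mean that participants will be told their arm or their interim results. The text does not support that. Sections 7.4.1 to 7.4.3 govern the blind separately, and asking participants to guess their condition shows that allocation is meant to be withheld. Feedback is offered as needed, and the only referral named is neuropsychological. The 4-week visit is optional in the Schedule of Events, and the questionnaire endpoints in 3.4.2 compare baseline with participation end. The point therefore shrinks to missing timing. Section 7.4.3 may be a more direct threat to the 4-week data if its participation end visit means treatment end. That is a separate question, and settling it would not fix when results may be fed back.

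**Conclusion.** The concern holds in limited form. The PI option in 7.4.1 contradicts the masking stated in the Protocol Summary and 3.3. Combined with the PI's part in referral and consent, it leaves concealment and investigator masking not assured. They are not shown to be absent.

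If the PI filled both roles throughout, the next assignment would be guessed correctly about 69% of the time instead of 50%, with about 6% certain. This assumes equally likely block sizes and 40 participants per stratum, neither of which the documents state.

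The feedback point is secondary: the timing is unstated, and early disclosure is neither planned nor excluded. A reader might want to turn it into an inflated false-positive rate. That would need a shift in self-report scores in one arm only, and the documents give no basis for its size. Without a treatment effect, feedback on change would be distributed alike in both arms unless the person giving it were unmasked and biased.

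**What to change.** **Section 7.4.1.** Delete the option for the PI, so that only the separate technician or the independent randomizer prepares conditions. State that this person takes no part in referral, eligibility, consent, treatment sessions or outcome assessment, and that those who do these tasks do not see past allocations. The Protocol Summary and 3.3 then agree with 7.4.1.

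**Section 10.3.2 (secondary).** State that the debriefing sentence does not cover allocation. State also that individual gait, balance and cognitive change results are given after the participant's last outcome assessment, except findings needed for safety or clinical referral.

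**Cost.** The first change is wording and a division of roles among staff the protocol already names. The second delays feedback on results by up to about 9 weeks from baseline.
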